The TELEhealth and Dashboard Activated Health Services outreach (TELE-DASH) study is a pragmatic randomized controlled trial of a quality improvement (QI) intervention of a prospective panel management intervention to optimize medical treatment for Veterans with heart failure with reduced ejection fraction (HFrEF) compared to the receipt of usual VA health care services over a 6-month period of observation. The study will incorporate the existing VA Academic Detailing Heart Failure Dashboard (ADHFD) to target actionable patients with gaps in performance measures for guideline-directed medical therapies (GDMT). Patients with HFrEF are optimally managed by cardiovascular specialty clinics. Typically, patients are referred to cardiology or heart failure (HF) clinics from primary care, emergency department, or post-hospitalization clinicians and scheduled into clinic grids. These patients may be lost to follow-up, not referred without prior HF hospitalization, or clinicians may miss opportunities to optimize GDMT for HFrEF. GDMT includes Class I indicated medications from the following classes: beta blockers (BB), angiotensin-converting enzyme inhibitor (ACE), angiotensin II receptor blockers (ARB), angiotensin receptor neprilysin inhibitor (ARNI), mineralocorticoid receptor antagonist (MRA), sodium-glucose cotransporter-2 inhibitor (SGLT2i).¹⁻³ The intervention is designed around prospective panel management clinics led by clinicians using impromptu patient telephone calls or electronic communications with existing responsible clinicians.

3 Study Objectives

The purpose of this study is to measure the effectiveness of proactive panel management clinics to optimize GDMT relative to usual care. The study will also evaluate secondary outcomes that signify improved outcomes such as reduced hospitalizations and mortality. The study will also evaluate clinician time per intervention relative to usual cardiology or HF clinic structure.

4 Study Methods

4.1 General Study Design and Plan

This is a randomized, pragmatic QI study designed to evaluate the effectiveness of proactive panel management to close gaps in evidence-based care for patients with HFrEF. We will use the VA's ADHFD to generate a list of actionable patients with HFrEF and left ventricular ejection fraction (LVEF) $\leq 35\%$. After identifying a cohort of HFrEF patients from the ADHFD, we will randomize individual patients on the actionable list to usual VA care or a novel proactive panel management clinic. Clinicians will be trained on how to use the dashboard information to identify opportunities for optimization based on detailed chart review. The proactive panel management intervention will use clinicians to perform an electronic chart review and call patients impromptu at their discretion to evaluate HFrEF management and opportunities to optimize GDMT. Each panel management clinic is staffed by a single cardiovascular clinician or trainee with cardiology (PI) supervision. All patients will receive chart review or telehealth notes brought to the attention of primary care and cardiology clinicians. Patients randomized to the intervention will only receive one chart review during a half-day panel management clinic with follow-up of any laboratory results or diagnostic tests as required and referral to HF or general cardiology clinic as deemed appropriate. The control arm consists of the usual delivery of health services with routine scheduled appointments for primary care or cardiology.

Outcomes will be assessed at 6-months from the last patient to receive the intervention. The study is powered to detect superiority of the intervention compared to usual care in optimizing GDMT for HFrEF. Treatment assignment is based on 1:1 randomization using fixed blocks (size=6) to assure an equivalent number of patients randomized to the intervention and usual care. Patients are randomized after a list of 300 actionable patients

are generated from the ADHFD. Study participant numbers will be assigned to the list of patients sorted by optimization scores in Excel. The supervising statistician (AA) will generate concealed randomization assignments by participant identification numbers. The randomization assignments will be merged with baseline study dataset and exported as password protected Excel and PDF documents. Study investigators will divide the intervention arm into lists of 10 to 15 per half-day clinic. Patients not receiving chart review or phone call attempts will be reassigned to future panel management clinics until all patients receive the intervention. Patients that did not answer phone calls will receive chart review notes for primary care and cardiology clinicians and not be reassigned to future panel management clinics.

Study participants do not require informed consent as determined by the VA IRB review. Patients will receive all accepted standards of care and medications approved by the Food and Drug Administration for HFrEF indications. The VA Subcommittee for Research and Safety found an absence of any declared research-laboratory-based biohazards and granted exemption from continued review. The study will evaluate the effectiveness of the QI intervention, telephone/telemedicine panel management clinics, to more rapidly implement evidence-based care for patients with HFrEF. Patients in the usual care arm will be unaware they are part of the control group for the RCT. Intervention patients nor study staff are blinded to usual care or intervention assignments. Patients that receive the intervention will be informed this is a pilot quality improvement effort with informal consent before proceeding to the clinical interventions. Intervention patients may refuse to participate after being contacted by phone in the intervention.

Study enrollment is based on the inclusion and exclusion criteria used to filter the ADHFD list. A list of actionable patients with HFrEF will be exported for randomization. The GDMT optimization score will be automated for each patient on the extracted list (**Table 1**). A sample of 300 patients will be selected with the lowest GDMT composite scores. Once the final sample of the study is determined, patients will be randomized to usual care or the intervention. Intervention patients will be divided into smaller lists of 10 to 15 patients. These smaller lists will be assigned to proactive panel management clinics. Clinicians staffing the intervention clinics will review ADHFD data, review the electronic health record (EHR) and decide whether to proceed to evaluate and recommend treatment over the phone to patients directly. If clinicians did not have sufficient time to review all patients on their clinic list, they will be redistributed to future intervention clinics. Intervention clinics will be held until each patient assigned the intervention has a chart review or attempted telephone contact. A failure to contact a patient will trigger a letter to a patient or electronic communication to their primary care or cardiology clinician.

Prior to each ADHFD telehealth clinic (half-day clinic lasting 4 to 4.5 hours), clinicians will be sent a secure email that will include a password-protected Excel document of 15 patients with exported clinical summary data from the ADHFD. Clinicians will be instructed to chart-review patients and decide if an opportunity exists to further optimize the receipt of GDMT. Clinicians will also be given a document providing guidance on the sequence of GDMT optimization based on latest guidelines and VA policies (Supplement S1 GDMT Guidance Document). If a patient does not qualify for further optimization (i.e. chart documentation of prior intolerance, patient preference), a short note in the electronic health record (EHR) will document the chart review and inform the primary care clinician that based on chart review, no opportunity currently exists but they may consider further GDMT titration in the future. If a patient appears to have an opportunity for further titration, the clinician is encouraged to call the patient to see if they are available to discuss their HF care. If the patient agrees, a telehealth visit will take place over phone or switch to video. A formal telehealth cardiology visit will occur at the time of care. If the patient is interested but does not have time for a visit, a brief telephone note will be placed and a request for a future cardiology clinic visit will be requested. If a formal telehealth visit occurs, clinicians will be asked to inquire about key details around medication titration (**Supplement S2 Interview**

Guide). The data from chart review and interviews will be documented on a password-protected Excel document (**Supplement S3** Clinician Documentation Form). Any medication addition or titration will have indicated laboratory labs ordered per usual care. Lastly, clinicians will also be asked to administer a short survey with each participant based on a template at the end of the call proactive phone call (**Supplement S2 Interview guide**). Primary care and regular cardiology clinicians will be notified of any changes in medication management in the EHR. The study's lead (BZ, AV) will be available by phone to answer questions or problems that arise during the clinic. Supervision of patient encounters by clinical pharmacists, medical trainees, or advanced practice nurse practitioners and study protocols will be BZ as the licensed and boarded general cardiologist.

4.2 Inclusion-Exclusion Criteria and General Study Population

This quality improvement (QI) initiative involves patients with heart failure with reduced ejection fraction (HFrEF) receiving care in the VA West Los Angeles (WLA). The criteria for eligible patients are:

Inclusion criteria:

- Facility: Greater Los Angeles, CA
- Division: All divisions within Greater Los Angeles
- Patient is eighteen years of age or older
- Patients has a primary diagnosis of HFrEF (last documented LVEF \leq 35% per ADHFD algorithms)
- Patient has an estimated GFR greater than or equal to 30 mL/min
- Patient lacks at least one active prescription of a beta-blocker, ACE/ARB/ARNI, MRA, or SGLT2i
- There are no cardiology appointments in the upcoming 2 weeks.

[figure not shown]
Exclusion criteria:

- Patient is currently hospitalized at WLA

4.3 Randomization and Blinding

Patients will be randomized 1:1 to intervention and usual care groups with all patients randomized at one time; given the target sample size of n=300 total patients, the sequence will be generated using permuted blocks of size 6 to ensure that an equal number of patients are randomized to panel management and usual care, maximizing efficiency (power). The randomization sequence will be concealed from the clinicians until after randomization has already been complete. Post-randomization, study staff will not be blinded to allocation. GLA IRB exemption was granted for consent of the low risk, non-experimental intervention. The intervention does not allow for blinding of participants in the intervention arm.

Figure 1: CONSORT Study Flow Diagram Template

5 Safety

Clinicians involved with the intervention will report acute kidney injury (AKI) defined as 25% decrease in GFR from baseline on follow-up labs (1-week for MRA and 1-2 weeks for ACE/ARB/ARNI) after a successful medication titration within the intervention group. Laboratory alerts will be followed by pilot study clinicians. Hospitalization related to adverse medication event (e.g. symptomatic hypotension, AKI, hyperkalemia) related to the intervention. Difference in mortality between intervention and usual care.

6 Adverse Events

Specific adverse events of interest include symptomatic hypotension documented in the EHR. Hospitalizations related to heart failure will be captured during the study end using the ADHFD. If patients were removed from the dashboard at 6 months, a chart review will be performed to abstract missing data.

7 References

8 Listing of Tables, Listings, and Figures

Figure 1: CONSORT Study Flow Diagram Template

8

9 Supplemental Material

S1: GDMT Guidance Document for LVEF ≤35%

I. Make a recommendation

Step 1: patient not at target ACE/ARB or beta-blocker

Initiate/titrate up ACE/ARB and/or beta blocker

- If signs of volume overload or HR<70 → ACE/ARB
- If signs of euvoolemia, HR>70, atrial fibrillation history, ventricular ectopy → Beta-blocker
- Age < 75, systolic BP>120 mm Hg, HR >70, normal renal function → Start both

Tailored based on patient's profile and history.

Step 2a: Transition ACE/ARB to ARNI

- Initiate ARNI once patient is taking equivalent dosing to lisinopril 20 mg daily

Step 2b: Initiate and titrate up aldosterone antagonist

- If K < 5 (helpful for hypokalemia)
- Well tolerated in low BP patients
- Check labs 3-7 days within initiation. Repeat labs monthly for the first 3 months.

Step 2c:

Initiate SGLT2i – empagliflozin 10mg daily

- Initiate earlier if A1C ≥7% or GFR 25-60 mL/min/1.73m² refer nephrology for SGLT2i
- Otherwise, add to cornerstone beta-blocker and RAAS inhibitor, ideally when dosing is stable.

II. Discuss instructions and precautions

[figure not shown]
Symptomatic hypotension, genital yeast infections (SGLT2i)

III. Recommended follow-up

Labs, diagnostic imaging or studies, new consults, follow-up appointments

Strategies for intolerance/symptomatic hypotension

- Reduce non-GDMT antihypertensives, half diuretic dose with initiation of RAAS inhibitor or SGLT2i.
- Consider insulin reduction for history hypoglycemic events with SGLT2i.
- Space out administration times for medications
- Move RAAS inhibitors to evening to peak during sleep
- Lower morning doses relative to evening doses

S2: Interview Guide

Introduction

Hello, I am Dr. _____ calling from the West LA VA Cardiology. We are piloting an effort to proactively reach out to Veterans with heart disease to see how they are doing and improve their medical therapies for heart failure. Is now a convenient time to discuss your heart medications?

- **Yes:** Thank you. Do you have access to a smartphone or computer? May we convert this visit to video?

- **No:** May we request a follow-up phone, video, or in-person visit with our heart failure clinic?

Yes: Thank you. [RTC WLA-Cardiomyopathy Clinic]

No: Thank you for your time. [Chart review note for PMD and last cardiology fellow/attending highlighting potential opportunity for further medication optimization]

Obtain history and assess functional NYHA class

1. How have you been feeling? Any change in [dyspnea/orthopnea/edema]?
2. What type of physical activities do you do regularly [walking, exercise, stairs]?
3. Do you know what medications you take for heart failure and how do manage your medications?
4. Have you had issues with any of heart failure medications in the past?
5. Do you check your home blood pressure and weights regularly? What are they?
6. Do you have issues with lightheadedness/dizziness or passing out?

Make recommendation

Optimization: I see that you might benefit from an increase in you _____ / I see that you might benefit from an additional medication _____/I see you may benefit from stopping one of your non-heart failure blood pressure medications. May we start that today and you can receive the medication in the mail or pick-up from your local VA clinic?

Hypervolemia: Increase diuretic regimen and refer for face to face visit within 1 week.

Discuss appropriate precautions with optimization

Dizziness, orthostasis, follow-up blood tests.

SGLT2i [genital yeast infections/hypoglycemia for IDDM]

Next steps

- Order medications
- Follow-up appointment
- Required labs
- BMP in one week (MRA), 1-2 weeks (ACE/ARB/ARNI)

Questions

Do you have any concerns related to medication change? Other questions?

Feedback

Thank you for your time. This was a call part of our pilot telephone heart clinic program. How would you rate your experience with the heart failure outreach today on a scale 1 to 10 (10 being very appreciated)? Any suggestions to improve the program?

S3: Clinician Documentation Form

Documentation survey which will guide clinician's chart review and patient conversation. The form will be password-protected and utilize checkbox and short answers for clinician ease.

Clinic Date	Clinician	Start Time	Homeless	Active Substance Use	Female	Last EF	Last cards appt	Last PCP appt
1/1/21	[name]	13:55	x	x	x	35-40%	1/1/21	1/1/21

Phone Call Time	NYHA Class	No Response
9 minutes	III	x

Reasons for no GDMT titration				
Prior intolerance	Prior adverse event	Patient declined	Patient concerned of side effects	Other
x	x	x	x	Cost

Actions Performed						
Number of Rx adjusted	Med adjustment	Labs ordered	Imaging / diagnostic tests	RTC	Patient Letter	Consults
3	Amlodipine stopped	x	x	x	x	x

Feedback	End Time	Comments
9	1415	Straight to voicemail

Clinician Documentation form definitions	
Clinic date	Date today, (mm/dd/yy)
Clinician	Name of clinician (Last, First)
Start Time	Military time at onset of pre-chart
Homeless	Is the veteran currently experiencing homelessness?
Active substance use	Is the veteran actively using substances?
Female	Sex as categorized in EHR
Last EF	Most recent left ventricular ejection fraction on transthoracic echocardiogram, %
Last cards appt	Date of last cardiology clinic visit, (mm/dd/yy)
Last PCP appt	Date of last PCP visit, (mm/dd/yy)
Phone Call Time	Duration of successful phone or video visit
NYHA Class	Based on patient's symptoms and chart review, (1-3)
No response	Indication if no response after 2 attempts
Patient requests later appointment	Indication if patient is interested in further discussion, but busy at this time. Check and order RTC cardiology
Reasons for no GDMT	
Prior intolerance	History of symptomatic bradycardia or hypotension on GDMT
Prior adverse event	History of hospitalization or angioedema related to GDMT titration. History of yeast infection while taking an SGLT2i inhibitor
Patient declined	Patient declined additional or higher doses of medications in the past
Patient concerned of side effects	Patient is concerned of side effects of GDMT
Other	Other reasons cited by patients or on chart review in the comments
Actions Performed	
# medication adjustments	Number of medications adjusted after this visit
Medication adjustment detail	Description of medication adjustment
Labs ordered	If laboratory tests ordered as part of today's plan
Imaging / diagnostic tests ordered	If imaging or diagnostic tests ordered as part of today's plan
RTC	If "return to clinic" order placed to patient's cardiology clinic
Patient Letter	Letter mailed to patient regarding following up with primary care or cardiology regarding heart failure.
New consults	If new consults placed as part of today's plan
Patient feedback	Self-reported experience of conversation and heart failure plan, on a scale of 1 to 10, where 1 means an awful experience and 10 means an exceptional experience
Time (end call)	Military time on completion of phone call
Comments	Noteworthy general observations not contained in fields regarding chart review or patient experience

## **2 Abbreviations and Definitions**

ACE	angiotensin-converting enzyme inhibitor
ADHFD	Academic Detailing Heart Failure Dashboard
AKI	acute kidney injury
ARB	angiotensin II receptor blockers
ARNI	angiotensin receptor neprilysin inhibitor
HF	heart failure
HFrEF	heart failure with reduced ejection fraction
LVEF	left ventricular ejection fraction
MRA	mineralocorticoid receptor antagonist
SGLT2i	sodium-glucose cotransporter-2 inhibitor

## **3 Introduction**

### **3.1 Preface**

The TELEhealth and Dashboard Activated Health Services outreach (TELE-DASH) study is a pragmatic randomized controlled trial of a quality improvement (QI) intervention of a prospective panel management intervention to optimize medical treatment for Veterans with heart failure with reduced ejection fraction (HFrEF) compared to the receipt of usual VA health care services over a 6-month period of observation. The study will incorporate the existing VA Academic Detailing Heart Failure Dashboard (ADHFD) to target actionable patients with gaps in performance measures for guideline-directed medical therapies (GDMT). Patients with HFrEF are optimally managed by cardiovascular specialty clinics. Typically, patients are referred to cardiology or heart failure (HF) clinics from primary care, emergency department, or post-hospitalization clinicians and scheduled into clinic grids. These patients may be lost to follow-up, not referred without prior HF hospitalization, or clinicians may miss opportunities to optimize GDMT for HFrEF. GDMT includes Class I indicated medications from the following classes: beta blockers (BB), angiotensin-converting enzyme inhibitor (ACE), angiotensin II receptor blockers (ARB), angiotensin receptor neprilysin inhibitor (ARNI), mineralocorticoid receptor antagonist (MRA), sodium-glucose cotransporter-2 inhibitor (SGLT2i). The intervention is designed around prospective panel management clinics led by clinicians using impromptu patient telephone calls or electronic communications with existing responsible clinicians.

### **3.2 Scope of the analysis**

The analyses will evaluate the effectiveness of proactive panel management clinics in optimizing the receipt of GDMT for patients with HFrEF compared to usual care at 6-months post-intervention for the final participant. The goal is to demonstrate that panel management clinics are more effective than usual care in optimizing care for patients with HFrEF that may be lost to follow-up or not referred for HF evaluation and treatment.

## **4 Study Objectives and Endpoints**

### **4.1 Study Objectives**

The purpose of this study is to measure the effectiveness of proactive panel management clinics to optimize GDMT relative to usual care. The study will also evaluate secondary outcomes that signify improved outcomes such as reduced hospitalizations and mortality. The study will also evaluate clinician time per intervention relative to usual cardiology or HF clinic structure.

## 4.2 Endpoints

### 4.2.1 Primary outcome

The primary outcome is active prescription of HFrEF therapies as summarized by the change in GDMT optimization potential score (Table 1) at final evaluation. The optimization potential score ranges from 0-10. Scores of 0 indicate a high potential for further optimization. The scoring system is defined in as follows:

	Points		
	None	Low Dose	Targeted Dose
ACE/ARB/ARNI	0	1	2
Beta-Blocker	0	1	2
MRA	0	1	2
ARNI	0	1	2
SGLT2i	0	-	2

As an example, a patient on target doses of beta-blocker and ARNI would receive but not an MRA or SGLT2i would receive a total of 6 optimization points. ARNI are recommended for patients with HFrEF on optimal doses of ACE/ARB. Since a clinician in the VA is recommended to optimize ACE/ARB and BB for outpatients prior to switching to an ARNI, two additional points are granted for this additional titration step giving the presents of an ARNI a total of 4 points to reflect the complexity of titration.

### 4.2.2 Secondary outcome

The secondary outcomes of the study will include the following at final evaluation:

1. Active prescriptions for individual classes of GDMT
  - a. ACE/ARB/ARNI
  - b. Beta-Blocker
  - c. MRA
  - d. ARNI
  - e. SGTL2i
2. Hospitalizations
  - a. Total number of any cause hospitalization
  - b. Total number of primary HF hospitalizations
  - c. Proportion of patients with any hospitalization
  - d. Proportion of patients with any HF hospitalization
3. Number of deaths
4. Clinician time spent per patient from opening chart to end of patient-specific intervention and documentation.
5. Health service efficiency
  - a. Number of patients reviewed or contacted per half-day clinic
  - b. Number of medication adjustments (stop, start, titration) per half-day clinic
  - c. Number of laboratory tests ordered per half-day clinic
  - d. Number of imaging/diagnostic procedures ordered per half-day clinic
  - e. Number of referrals for consults/device therapy per half-day clinic
6. Qualitative evaluation of patient surveys who received the intervention.

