### I. Make a recommendation

Step 1: patient not at target ACE/ARB or beta-blocker

Initiate/titrate up ACE/ARB and/or beta blocker

- If signs of volume overload or HR<70 → ACE/ARB
- If signs of euvoemia, HR>70, atrial fibrillation history, ventricular ectopy → Beta-blocker
- Age < 75, systolic BP>120 mm Hg, HR >70, normal renal function → Start both

*Tailored based on patient's profile and history.*

Step 2a: Transition ACE/ARB to ARNI

- Initiate ARNI once patient is taking equivalent dosing to lisinopril 20 mg daily

Step 2b: Initiate and titrate up aldosterone antagonist

- If K < 5 (helpful for hypokalemia)
- Well tolerated in low BP patients
- Check labs 3-7 days within initiation. Repeat labs monthly for the first 3 months.

Step 2c:

Initiate SGLT2i – empagliflozin 10mg daily

- Initiate earlier if A1C ≥7% or GFR 25-60 mL/min/1.73m^2 refer nephrology for SGLT2i
- Otherwise, add to cornerstone beta-blocker and RAAS inhibitor, ideally when dosing is stable.

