### S3: Clinician Documentation Form

Documentation survey which will guide clinician's chart review and patient conversation. The form will be password-protected and utilize checkbox and short answers for clinician ease.

Clinic Date	Clinician	Start Time	Homeless	Active Substance Use	Female	Last EF	Last cards appt	Last PCP appt
1/1/21	[name]	13:55	x	x	x	35-40%	1/1/21	1/1/21

Phone Call Time	NYHA Class	No Response
9 minutes	III	x

Reasons for no GDMT titration				
Prior intolerance	Prior adverse event	Patient declined	Patient concerned of side effects	Other
x	x	x	x	Cost

Actions Performed						
Number of Rx adjusted	Med adjustment	Labs ordered	Imaging / diagnostic tests	RTC	Patient Letter	Consults
3	Amlodipine stopped	x	x	x	x	x

Feedback	End Time	Comments
9	1415	Straight to voicemail

Clinician Documentation form definitions	
Clinic date	Date today, (mm/dd/yy)
Clinician	Name of clinician (Last, First)
Start Time	Military time at onset of pre-chart
Homeless	Is the veteran currently experiencing homelessness?
Active substance use	Is the veteran actively using substances?
Female	Sex as categorized in EHR
Last EF	Most recent left ventricular ejection fraction on transthoracic echocardiogram, %
Last cards appt	Date of last cardiology clinic visit, (mm/dd/yy)
Last PCP appt	Date of last PCP visit, (mm/dd/yy)
Phone Call Time	Duration of successful phone or video visit
NYHA Class	Based on patient's symptoms and chart review, (1-3)
No response	Indication if no response after 2 attempts
Patient requests later appointment	Indication if patient is interested in further discussion, but busy at this time. Check and order RTC cardiology
Reasons for no GDMT	
Prior intolerance	History of symptomatic bradycardia or hypotension on GDMT
Prior adverse event	History of hospitalization or angioedema related to GDMT titration. History of yeast infection while taking an SGLT2i inhibitor
Patient declined	Patient declined additional or higher doses of medications in the past
Patient concerned of side effects	Patient is concerned of side effects of GDMT
Other	Other reasons cited by patients or on chart review in the comments
Actions Performed	
# medication adjustments	Number of medications adjusted after this visit
Medication adjustment detail	Description of medication adjustment
Labs ordered	If laboratory tests ordered as part of today's plan
Imaging / diagnostic tests ordered	If imaging or diagnostic tests ordered as part of today's plan

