RTC	If "return to clinic" order placed to patient's cardiology clinic
Patient Letter	Letter mailed to patient regarding following up with primary care or cardiology regarding heart failure.
New consults	If new consults placed as part of today's plan
Patient feedback	Self-reported experience of conversation and heart failure plan, on a scale of 1 to 10, where 1 means an awful experience and 10 means an exceptional experience
Time (end call)	Military time on completion of phone call
Comments	Noteworthy general observations not contained in fields regarding chart review or patient experience

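### Secondary outcomes 5c to 5e are worded as counts of orders, but the only data form described records them as yes/no, so that form can give only the number of patients with any order

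*SAP*

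**What the plan says.** SAP 4.2.2, item 5 (health service efficiency), lists three outcomes whose unit is an order:

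- 5c: "Number of laboratory tests ordered per half-day clinic"
- 5d: "Number of imaging/diagnostic procedures ordered per half-day clinic"
- 5e: "Number of referrals for consults/device therapy per half-day clinic"

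SAP 5.1 sends the data from chart review and interviews to the clinician documentation form, S3. That form has a block for actions performed, with fields that parallel these outcomes. Its definitions read:

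- Labs: "If laboratory tests ordered as part of today's plan"
- Imaging and diagnostics: "If imaging or diagnostic tests ordered as part of today's plan"
- Consults: "If new consults placed as part of today's plan"

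The medication field in the same block is defined as a number. The copy of S3 in Protocol section 9 has the same definitions. No field in either copy is for device therapy.

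SAP 5.4 names the ADHFD as the main data source. Neither its list of variables nor Table 2 (SAP 8.4) includes orders or referrals. SAP 7.4 provides for chart review where data needed for primary or secondary analyses are missing from the ADHFD. SAP section 9 gives no derivation or analysis for 5c to 5e.

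**The concern.** The outcomes and the form use different units. An outcome that counts tests needs a number for each patient, and a tick says only that the number is at least one. Adding ticks over a half-day clinic gives the number of patients with any order. Published as a number of tests, that figure would be mislabelled, and it would be too low whenever a patient has two or more orders of the same kind.

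These are the only listed outcomes that describe the testing and referral load of a panel clinic. Someone planning laboratory or imaging capacity for a similar service would use them, and would need to know whether they count orders or patients.

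**Working it through.** The plan states no figure for 5c to 5e, so there is nothing to reproduce. The check sets the outcomes against the possible sources and then sizes the gap under stated assumptions.

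**Step 1. Units.**

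| Outcome (SAP 4.2.2) | Unit needed | S3 field | Count available from S3? |
|---|---|---|---|
| 5b medication adjustments | number | number | yes |
| 5c laboratory tests | number | yes/no | no |
| 5d imaging/diagnostic procedures | number | yes/no | no |
| 5e consult/device referrals | number | yes/no for consults; no device field | no |

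**Step 2. Other sources.** The ADHFD variables in SAP 5.4 and Table 2 contain no orders or referrals. Chart review (SAP 7.4) could supply them. SAP 7.1 and 8.1 describe chart review for patients who have dropped off the dashboard. No section describes a review of orders for all of the roughly 150 intervention patients (300 randomized 1:1).

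**Step 3. Size if S3 is the source.** Inputs:

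- n = patients on a clinic list, 10 to 15 (SAP 5.1)
- p = share of them with any order of a given kind (not in the documents; assumed)
- m = mean orders of that kind per patient with any (not in the documents; assumed range 1 to 4)

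Form total: F = n × p. Number of orders: T = n × p × m. Share missed: 1 - F/T = 1 - 1/m, which depends on neither n nor p.

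| m (assumed) | Share missed |
|---|---|
| 1 | 1 - 1/1 = 0% |
| 1.5 | 1 - 1/1.5 = 33% |
| 2 | 1 - 1/2 = 50% |
| 4 | 1 - 1/4 = 75% |

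Example with n = 15, p = 0.5 and m = 2: F = 15 × 0.5 = 7.5, against T = 15 × 0.5 × 2 = 15.

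Since p cannot exceed 1, F cannot exceed n. Each of 5c, 5d and 5e is therefore capped at 10 to 15 per clinic, whatever was ordered.

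**Step 4. Is m above 1 plausible?** For labs, it can be. The guidance in S1 for an aldosterone antagonist names a check 3 to 7 days after initiation and then "Repeat labs monthly for the first 3 months". That would be 1 + 3 = 4 checks if all were ordered on the clinic day, which is an assumption. The next-steps list in S2 names a single metabolic panel after an MRA change; if only that is ordered, m = 1 for such patients. For imaging and consults the documents give nothing from which to judge m.

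**The case against.** The strongest reply is that no section says 5c to 5e will be derived from S3. A reader might infer that S3 is the sole source and that the counts cannot be recovered. The documents do not support that. S3 is the only form described, which is not the same thing, and SAP 7.4 read literally covers data that secondary outcomes need and the ADHFD lacks. S3 also has a free-text comments field and allows short answers. This stands, so the undercount is conditional. It does not remove the mismatch: if chart review is the intended source, the SAP should say so and apply it to the whole intervention arm.

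A reader might also infer a fourfold undercount of labs from the S1 schedule. That needs every repeat check to be ordered on the clinic day, and S3 asks only about that day's plan. With one order per patient the loss is zero. The documents do not say whether a test means an order, a draw or an analyte.

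A third inference would be that the panel clinic will look less demanding than usual care. No comparator is planned for 5c to 5e. The comparison with usual HF clinics in SAP 9.3 covers medication titrations, which S3 records as a number.

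It is also fair to say that the sample row in S3 is weak evidence. It is a mock entry that marks no response beside a 9-minute call. The point rests on the field definitions, which are clear. S3 does record return-to-clinic orders separately, so some referral activity is captured outside the consult box, but that does not turn the box into a count.

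**Conclusion.** The mismatch holds for all three outcomes. As written, S3 cannot yield the stated counts and the dashboard does not hold them. If S3 is the source, each result is the number of patients with any order, capped at 10 to 15 per clinic, and the share of orders missed is 1 - 1/m: 0% at m = 1, 50% at m = 2 and 75% at m = 4. Because m is not in the documents, the size is a range that starts at zero and not an established understatement. Device referrals could be missed altogether if clinicians do not enter them as consults.

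Severity is low. The three outcomes are descriptive and arise only in the intervention arm. The primary outcome, power, outcomes 5a and 5b, and clinician time are unaffected.

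**What to change.** **If clinics have not yet run:** in S3 (both the Protocol and SAP copies), change the labs, imaging/diagnostic and consult fields from yes/no to a number, as the medication field already is. State that device-therapy referrals are included in the consult number, and say in one line what counts as one test. The cost is three field definitions on an Excel form and a few seconds per patient.

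**If clinics have already run on the present form,** choose one of these and write it into SAP 4.2.2:

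- Take the counts from EHR orders for every intervention patient and name that as the source. This costs an order extract or chart abstraction for about 150 patients.
- Restate 5c to 5e as the number and proportion of patients with at least one laboratory, imaging/diagnostic or consult order per half-day clinic. This costs three reworded lines and no new data, provided device referrals were ticked as consults; if that is uncertain, drop device therapy from the wording of 5e.
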